## 9.2 EFFICACY ASSESSMENTS

Not Applicable.

## 9.3 PHARMACOKINETIC ASSESSMENTS

### Pharmacokinetic Sampling

Blood and breast milk samples will be taken from the mother for measurement of  $\alpha$ GAL concentrations. Sample collection, processing, and shipping instructions are provided in the SOM.

Blood samples will be taken from the mother at Months 1, 3, and 6 for PK testing (if mother is lactating at the time of the evaluation and is receiving Fabrazyme therapy). Blood samples will be collected prior to each breast milk collection as follows: sample 1: immediately prior to Fabrazyme infusion and prior to breast milk collection; sample 2: just prior to the end of Fabrazyme infusion and prior to breast milk collection; and sample 3: 2 hours after Fabrazyme infusion and prior to breast milk collection.

Bioanalytical Method.

### Pharmacokinetic parameters

The following pharmacokinetic parameters will be calculated, using noncompartmental methods from plasma  $\alpha$ GAL concentrations and milk  $\alpha$ GAL concentrations

- maximum plasma concentration observed ( $C_{max}$ ) in plasma and milk
- area under the plasma  $\alpha$ GAL concentration versus time curve calculated using the trapezoidal method from 0 to 2 hours post end of infusion ( $AUC_{0-2 \text{ plasma}}$ ).

- The amount of  $\alpha$ GAL in milk calculated as the product of  $\alpha$ GAL activity times the milk volume
- area under the milk  $\alpha$ GAL concentration versus time curve calculated using the trapezoidal method from 0 to 2 hours post end of infusion ( $AUC_{0-2 \text{ milk}}$ ).
- Lactation clearance determined in the 0-2 hours interval, according to the following equation : amount of  $\alpha$ GAL excreted over the sampling period divided by the AUC during the sampling period

The milk to plasma ratio for  $AUC_{0-2}$  will also be computed.

## 9.4 SAFETY ASSESSMENTS AND OTHER MEASUREMENTS

### 9.4.1 Adverse Events

An AE is any undesirable physical, psychological, or behavioral effect experienced by a patient or subject during their participation in an investigational study whether or not product-related. This includes any untoward signs or symptoms experienced by the mother and/or infant from the time of signing of the informed consent until completion of the study. AEs may include, but are not limited to:

- Subjective or objective symptoms spontaneously demonstrated by the infant and/or observed by the mother, guardian, investigator, or medical staff.
- Laboratory abnormalities of clinical significance.

Disease signs, symptoms, and/or laboratory abnormalities already existing prior to the use of the study medication are not considered AEs after treatment unless they reoccur after the patient has recovered from the pre-existing condition or they represent an exacerbation in intensity or frequency.

All AEs ongoing at the time of withdrawal, study termination, or study completion require a follow up at approximately 28 days after discontinuation of study participation. The Investigator will be asked to follow-up on all SAEs that were ongoing at the time of withdrawal, termination or completion until resolution, until both the sponsor and investigator agree follow-up is deemed no longer medically necessary or until the patient is lost to follow-up.

If any new SAEs are identified during the course of this follow-up of ongoing SAEs, additional follow-up of these new SAEs may be performed. The Investigator and sponsor will determine if the follow-up is clinically warranted and relevant to the evaluation of the safety of the trial treatment or until patient is lost to follow up. The investigator must follow patients with AEs until their condition resolves or stabilizes. Certain conditions that are not expected to resolve, such as metastatic cancer, need not be followed indefinitely by the investigator.

#### 9.4.2 Serious Adverse Events

SAEs will be recorded from signed consent through the Month 24 visit (or through the Month 6 visit if only the mother is participating in the study). For patients who discontinue prematurely from the study, SAEs will be reported from signed consent through the last patient study visit. A serious adverse event is defined as any AE that results in any of the following outcomes:

- Death
- Life-threatening experience
- Required or prolonged inpatient hospitalization
- Persistent or significant disability/incapacity
- Congenital anomaly/birth defect
- Important medical events, based upon appropriate medical judgment, that may jeopardize the patient or subject and may require medical or surgical intervention to prevent 1 of the outcomes listed above

Life-threatening experience: any AE that places the patient, in the view of the reporter, at immediate risk of death from the AE as it occurred, ie, does not include an AE that had it occurred in a more severe form might have caused death.

Persistent or significant disability/incapacity: the AE that resulted in a substantial disruption of a person's ability to conduct normal life functions.

Important medical events based upon appropriate medical judgment, that may jeopardize the patient or subject and may require medical or surgical intervention to prevent one of the outcomes listed above: an AE that may not result in death, be life-threatening, or require hospitalization may be considered an SAE when, based upon appropriate medical judgment, it may jeopardize the patient or subject and may require medical or surgical intervention to prevent one of the outcomes listed above.

The Investigator will be asked to assess the severity of the adverse drug/biologic event using the following categories: Mild, Moderate, and Severe. This assessment is subjective and the Investigator should use medical judgment to compare the reported AE to similar types of events observed in clinical practice. Below are listed guidelines for severity assessment:

**Mild:** Symptom(s) barely noticeable to the subject/patient or does not make the subject/patient uncomfortable. The AE does not influence performance or functioning. Prescription drugs are not ordinarily needed for relief of symptom(s).

**Moderate:** Symptom(s) of a sufficient severity to make the subject/patient uncomfortable. Performance of daily activities is influenced. Treatment of symptom(s) may be needed.

**Severe:** Symptom(s) of a sufficient severity to cause the subject/patient severe discomfort. Severity may cause cessation of treatment with the study drug. Treatment for symptom(s) may be given.

### **9.4.3 Adverse Event and Serious Adverse Event Reporting**

All SAEs will be documented on the study CRF and reported within 24 hours of the Study Investigator's knowledge of the event, even if the experience does not appear to be related to Fabrazyme. The following central global contact information should be used for reporting to the Sponsor's Global Pharmacovigilance and Epidemiology (GPE):

[contact]

Email: [contact]

For all SAEs, a detailed written description that includes copies of relevant patient records, autopsy reports, and other documents will be sent to Sponsor's Global Pharmacovigilance and Epidemiology (GPE) Department as directed above.

During the course of the study, Sanofi Genzyme is responsible for reporting in an expedited manner all SAEs that are both unexpected and at least reasonably related to the study drug to the regulatory authorities, independent ethics committee (IECs)/institutional review boards (IRBs) as appropriate, and to the Investigators. Additionally, Sanofi Genzyme is responsible for expedited reporting of all SAEs that are expected and at least reasonably related to the study drug to the regulatory authorities, according to the local regulations.

### **9.4.4 Clinical Laboratory Tests**

Not applicable.

### **9.4.5 Concomitant Medications**

A concomitant medication is any medication, prescription or over the counter, taken by a patient during their participation in an investigational study. All medications taken from the time of signing the Informed Consent through to study completion will be recorded on the CRF. In addition, at every visit, the site personnel will record any medication used by the patient since a previous visit.

Administration of concomitant medication(s) signals that an AE should be recorded.

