
CRITERIA FOR EVALUATION:
 
Mother
 
 
• Efficacy: Efficacy will not be measured in this study.
 
• Pharmacokinetics: Blood and breast milk samples will be taken from the mother at Months 1, 3, and 6 for measurement of αGAL concentrations (if mother is lactating at the time of the evaluation and is receiving Fabrazyme therapy). Blood samples will be collected prior to each breast milk collection as follows: sample 1: immediately prior to Fabrazyme infusion and prior to breast milk collection; sample 2: just prior to the end of Fabrazyme infusion and prior to breast milk collection; and sample 3: 2 hours after Fabrazyme infusion and prior to breast milk collection. Breast milk samples will be collected after each plasma collection for PK testing as follows: sample 1: immediately prior to Fabrazyme infusion and after plasma collection; sample 2: immediately after Fabrazyme infusion and after plasma collection; and sample 3: 2 hours after Fabrazyme infusion and after plasma collection. The volume of breast milk expressed from each timepoint (immediately prior to infusion, from infusion start until end of infusion, and from end of infusion until 2 hours post-infusion) will be recorded and summarized.
 
• Breast Milk: Samples of expressed breast milk will be collected by pump at Months 1, 3, and 6 (if mother is lactating at the time of the evaluation and continues to receive Fabrazyme therapy) for PK assessment as above. Additionally, the volume, fat content, and protein content of breast milk samples will be determined.
 
• Safety: The IgG antibody titers and incidence of adverse events (AEs) occurring in mothers enrolled in this study will be summarized.
 
 
Infant
 
 
• Efficacy: Efficacy will not be measured in this study.
 
• Immunoglobulins: At birth, a sample of umbilical cord blood will be collected to determine the infant's Baseline anti-r-hαGAL IgM and IgG titers. Testing for presence of IgG and IgM antibodies will also occur at Month 2, 6, and 12.
 
• Development: The infant's growth and development will be monitored from birth to Month 24 through physical exams and the Denver II Developmental Screening Test.
 
• Safety: The incidence of adverse events occurring in infants enrolled in this study will be summarized.
 
 
Genotype testing: will be conducted for all participating infants on umbilical cord blood to determine diagnosis of Fabry disease. In cases when umbilical blood cord sample is not collected at the Baseline visit, genotyping of the infant enrolled for full participation could be performed on the additional blood sample collected at visit month 12. If genotyping of the infant is performed as a part of standard care prior to visit month 12, this result will be recorded by Investigator in the CRF (Case Report Form).
		

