## **8.5 PRIOR AND CONCOMITANT MEDICATIONS**

All medications taken by the mother and all medications taken by the infant from the time the Informed Consent Form is signed until the end of study participation will be recorded on the Concomitant Medication CRF.

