2.4.5.1 Analyses of adverse events

Generalities

All adverse events (AEs) reported from signing of informed consent through completion of the study will be presented.

Adverse event incidence tables will present by SOC and PT, sorted in alphabetical order for each group (mother, infant), the number (n) and percentage (%) of patients experiencing an adverse event. Multiple occurrences of the same event in the same patient will be counted only once in the tables within the study period. The denominator for computation of percentages is the safety population within each group (mother, infant).

Sorting within tables ensures the same presentation for the set of all adverse events within the observation period. For that purpose, the table of all adverse events presented by SOC and PT sorted by the internationally agreed SOC order and decreasing frequency of PTs within SOC will define the presentation order for all other tables unless otherwise specified.

Analysis of all adverse events

The following adverse event summaries will be generated for the safety population.

- Overview of adverse events, summarizing number (%) of patients with any
 - adverse event
 - serious adverse event
 - adverse event leading to death
 - adverse event leading to permanent treatment discontinuation
- All adverse events by primary SOC and PT, showing the number (%) of patients with at least 1 adverse event, sorted by the internationally agreed SOC order and by decreasing incidence of PTs within each SOC. This sorting order will be applied to all other tables, unless otherwise specified
- All adverse events regardless of relationship and related to IMP, by primary SOC and PT, showing the number (%) of patients with at least 1 adverse event
- All adverse events by maximal severity, presented by primary SOC and PT, showing the number (%) of patients with at least 1 adverse event by severity (ie, mild, moderate, or severe)

Analysis of all treatment emergent serious adverse event(s)

- All serious adverse events by primary SOC and PT, showing the number (%) of patients with at least 1 serious adverse event
- All serious adverse events regardless of relationship and related to IMP, by primary SOC and PT, showing the number (%) of patients with at least 1 serious adverse event

- All serious adverse events by maximal severity, presented by primary SOC and PT, showing the number (%) of patients with at least 1 serious adverse event by severity (ie, mild, moderate, or severe)

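### Protocol 9.4.5 ties AE recording to the giving of any concomitant medication, which conflicts with the AE definition in 9.4.1 and could inflate AE incidence if applied literally

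*Protocol*

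**What the plan says.** Protocol 9.4.5 sets a broad scope: "A concomitant medication is any medication, prescription or over the counter, taken by a patient during their participation in an investigational study". The same section ends with the sentence at issue: "Administration of concomitant medication(s) signals that an AE should be recorded". It is not limited to new medicines, to changes of dose or to particular indications.

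Protocol 8.5 sets who and when: "All medications taken by the mother and all medications taken by the infant from the time the Informed Consent Form is signed" are recorded until participation ends. For infants in full participation, the Baseline section (9.1.1.1) starts the record at consent or birth.

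Protocol 9.4.1 defines the event itself: "An AE is any undesirable physical, psychological, or behavioral effect experienced by a patient or subject during their participation in an investigational study". It adds that signs, symptoms and laboratory abnormalities "already existing prior to the use of the study medication are not considered AEs after treatment unless they reoccur" after recovery or become more intense or frequent.

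The synopsis lists one item under Safety for infants: "The incidence of adverse events occurring in infants enrolled in this study will be summarized". For mothers it lists two, IgG titers and AE incidence. SAP 2.4.5.1 tabulates all AEs reported from consent to study completion as numbers and percentages of the safety population, separately for mothers and infants.

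**The concern.** Taken at its word, the last sentence of 9.4.5 makes the giving of a medicine sufficient reason for an AE record. A mother who continues a long-standing medicine for an unchanged condition has no AE under 9.4.1, yet 9.4.5 says that one should be recorded. The same applies to an infant given a preventive product with no sign or symptom. Neither section says which prevails.

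The study has no reference treatment and no hypothesis test, so the safety output is an absolute incidence in a single group. Over-recording cannot cancel between arms. With about 10 mothers and up to 10 infants, one patient is about 10 percentage points (1/10). With about 10 centers for about 10 mothers, a site contributes about one mother on average (10/10). A difference in how sites read the sentence would then be hard to tell apart from a difference between patients.

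**Working it through.** The documents state no expected AE rate, medication rate, power or calculated sample size. There is no figure of the plan's own to reproduce, and the check is mainly a comparison of text.

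**1. Trigger against definition.** In 9.4.5 the trigger is administration; in 9.4.1 it is an undesirable effect. The two agree when a medicine treats a new or worsened condition. They disagree when it is prophylactic, routine, or for an unchanged pre-existing condition.

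**2. Other triggers in the protocol.** Section 9.4.8 turns a physical finding into an AE only on clinically significant worsening from Baseline, and it defines clinical significance. Section 9.4.5 has no such limit.

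**3. Downstream steps.** SAP 2.4.5.1 presents every reported AE. It counts a patient once per event, which limits repeat counting but removes neither a false term nor a patient wrongly counted as having any AE. SAP 2.5.3 counts an AE with missing causality as related, so such a record could also reach the related-AE tables. With fewer than 5 mothers and/or 5 infants, SAP 2.4 moves to listings, which would still show these records.

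**4. Illustration of size.** The inputs are assumptions:
- p is the true share of patients with at least one AE.
- q is the share with at least one medicine not prompted by an AE and recorded as an AE under the literal reading. Where only some sites read it that way, q is correspondingly smaller.
- p and q are independent, and n = 10 per group.

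Reported share = 1 − (1 − p)(1 − q). For p = 30% and q = 50%: 1 − 0.70 × 0.50 = 65%. Extra patients = 10 × (0.65 − 0.30) = 3.5.

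| True share p | q = 50% | q = 80% | q = 100% | Extra patients of 10 |
|---|---|---|---|---|
| 30% | 65% | 86% | 100% | 3.5 to 7 |
| 50% | 75% | 90% | 100% | 2.5 to 5 |
| 70% | 85% | 94% | 100% | 1.5 to 3 |
| 90% | 95% | 98% | 100% | 0.5 to 1 |

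The reported share is never below p, so the direction is fixed. The size depends wholly on p and q. If nearly every patient has a true AE during up to 24 months of monitoring, the any-AE percentage has little room to rise. The distortion would then lie in the preferred-term and related-AE counts.

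**The case against.** The best reply is that 9.4.5 does not redefine an AE. Its verb can be read as a prompt to look for an event, with 9.4.1 deciding whether there was one. The rest of the process fits that reading. Severity is graded by symptoms and effect on functioning (Protocol 9.4.2), each AE is coded to MedDRA terms (SAP 2.1.4.1), and CRFs are monitored, source-verified and queried (Protocol 10.2). A preventive product given to a well infant offers no effect to grade. Protocol 10.3 also has clinical and statistical staff decide on inclusion and exclusion of data before lock.

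Much of this stands. It makes wholesale recording of non-events unlikely, and a reader who infers that routine medicines will all become AEs goes further than the documents allow. It does not remove the conflict, because the sentence says an AE should be recorded, not considered. The provision in 10.3 is general and gives no rule for such records.

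A reader might also infer that the study's main safety result is at risk. No document gives AE incidence that label. Protocol 9 lists AEs beside concomitant medication, immunogenicity, vital signs and physical examination including growth and development. None of the three objectives mentions AEs. It is equally too strong to say that counts from different sites could not be pooled: the tables are descriptive, and no between-site analysis is planned.

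**Conclusion.** The point holds as a wording conflict with a possible effect on counts. Read literally, 9.4.5 asks for AE records that 9.4.1 would not support, and the SAP sets no step that would take them out. AE incidence could be overstated, and sites could differ in what they record.

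The direction is upward. The size cannot be established from the documents, and the percentages above are illustrations under assumed, independent rates. In particular, an overstatement of 30 to 70 percentage points, which a reader might infer from true rates of 70% down to 30%, needs every patient to receive a medicine not prompted by an AE and every site to apply the literal reading. The documents support neither assumption. At a true rate of 90% the gain is at most 10 points.

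No test, error rate or sample size is affected, and the objectives on milk αGAL activity, milk production and composition, and infant growth, development and immune response do not rest on AE counts. The correction is still worth making, because a single-arm incidence in about 10 patients per group has nothing to offset over-recording.

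**What to change.** Replace the last sentence of Protocol 9.4.5 with text to this effect:

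*For each concomitant medication, record the indication and check whether an event meeting the definition in Section 9.4.1 occurred. Record an AE only if it did. Medicines given for prophylaxis, as routine care, or for an unchanged pre-existing condition do not by themselves create an AE record.*

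Carry the same wording into the CRF completion guidance, and confirm that the Concomitant Medication CRF captures the indication. Rewording does not reach records already made, so a short pre-lock check under Protocol 10.3 could query any AE record that names a medicine but no sign, symptom or condition.

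The cost is a sentence or two in the protocol and a matching line in the CRF guidance. No planned table or sample size changes.

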### **9.4.6 Status of Lactation/Receiving Breast Milk**

Whether or not the mother is lactating will be recorded at each visit on the mother's CRF.

If the infant is participating in this study, whether or not the infant is receiving breast milk will be recorded at each visit on the infant's CRF.

#### **9.4.7 Breast Milk Samples**

Breast milk samples of mothers receiving Fabrazyme will be tested for  $\alpha$ GAL activity, volume, and fat and protein content. Since  $\alpha$ GAL is a protein, it is a normal component of breast milk and it is possible that the women enrolled in the study naturally produce  $\alpha$ GAL in the breast milk samples. The current assay cannot differentiate between endogenous  $\alpha$ GAL and Fabrazyme. As breast milk samples are not available prior to the mother having started Fabrazyme therapy, breast milk samples will be tested just prior to the Fabrazyme infusion and at timed intervals as specified above (see [Section 9.3](#)) to see if there is an increase in the  $\alpha$ GAL levels in breast milk.

Each breast milk collection should first be measured for total volume. An aliquot of each breast milk sample collected at the site is to be set aside for testing and the remainder of the sample may be fed to the infant. Refer to the SOM for further details on breast milk sampling.

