
STATISTICAL AND ANALYTICAL PLANS:
 
Statistical Methods: Data collected in this study will be analyzed using descriptive statistics and reported using summary tables, graphs, figures, and/or patient data listings. No hypothesis testing will be performed. Details of the statistical analysis will be specified in the Statistical Analysis Plan.
 
Study Variables
 
Mother: The following study variables from the mothers will be summarized:
 
 
● Plasma αGAL activity
 
● Milk αGAL to plasma αGAL ratio;
 
● The levels of αGAL activity, volume, total fat and protein content in breast milk samples;
 
● Lactation status;
 
● Frequency of AEs, coded using the Medical Dictionary for Regulatory Activities (MedDRA);
 
● Concomitant medications received.
 
 
Each lactating woman will serve as her own control, with pre-infusion and post-infusion breast milk samples. The following data will be collected through the Registry and summarized:
 
 
● Medical history (including Fabrazyme status during pregnancy);
 
● Genotyping;
 
● Pregnancy outcomes;
 
● IgG antibody.
 
 
Infant: The following study variables from the infants will be summarized:
 
 
● Medical history;
 
● Physical exam;
 
● Gender;
 
● Apgar scores at 1 minute and 5 minutes after birth;
 
● Denver II Developmental Screening Test;
 
● IgM antibody titer to r-hαGAL;
 
● IgG antibody titer to r-hαGAL;
 
● Genotype;
 
● Frequency of AEs, coded using MedDRA;
 
● Concomitant medications received.
 
 
Sample Size: No formal statistical sample size calculations were performed for this study. The sample size of approximately 10 mothers and up to 10 infants is based upon 1) the availability of mothers to study lactation in this rare disease and 2) the availability of infants whose parents or legal guardians consent to their participation in this study.
 
Interim Analysis: After 5 mothers have contributed breast milk samples to this study, an interim analysis of αGAL activity in the breast milk will be performed. [REDACTED]
 
In addition, status of this study will be summarized annually as part of the Fabry Registry Program Annual Report.
		

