## **11.8 SAFETY ANALYSIS**

The following study variables will be summarized as appropriate for the mothers:

- Medical history (including Fabrazyme status during pregnancy)
- Genotyping
- Pregnancy outcome
- IgG antibody status
- Lactation status
- Plasma and breast milk PK testing
- The level of  $\alpha$ GAL, volume, and fat and protein content in breast milk samples
- Frequency of AEs
- Frequency of concomitant medications

The following study variables will be summarized as appropriate for the infants:

- Medical history
- Physical examination
- Gender
- Genotype
- Apgar score at 1 minute and 5 minutes after birth
- Denver II Developmental Screening Test
- IgM antibodies to r-h $\alpha$ GAL – presence, time to development, level of titers present
- IgG antibodies to r-h $\alpha$ GAL – presence, time to development, level of titers present
- Frequency of AEs
- Frequency of concomitant medications

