## 11.10 PHARMACOKINETICS ANALYSIS

Because of the limited sampling schedule, the only PK parameters that will be reported are maximum concentration ( $C_{max}$ ) and area under the plasma  $\alpha$ GAL concentration-time curve (AUC) from 0 to 2 hours post end of infusion ( $AUC_{0-2}$ ). A more complete PK profile is not being done because it is not the objective of the study to characterize the pharmacokinetics of  $\alpha$ GAL in lactating mothers.

Lactation clearance will be determined using the same calculations used to assess renal clearance. Breast milk will be collected at Baseline (sample 1) to empty each breast of milk, at end of infusion (sample 2), and 2 hours post-dose (sample 3). The amount of  $\alpha$ GAL will be calculated as the product of  $\alpha$ GAL activity times the milk volume. AUC from Baseline to 2 hours after the end of infusion will be calculated using a linear trapezoid. Lactation clearance will be estimated as the amount of  $\alpha$ GAL excreted over the sampling period divided by the AUC during the sampling period. The milk to plasma ratio calculated as the  $AUC_{milk}$  to  $AUC_{plasma}$  from time 0 (sample 2) to 2 hours after the end of infusion (sample 3) will also be computed.

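### The visible analysis text never carries out the pre- versus post-infusion comparison on which the protocol relies, so the stated milk αGAL parameters cannot by themselves show drug transfer; the lactation clearance interval is also stated in two conflicting ways

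*Protocol*

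**What the plan says.** **How milk αGAL is to be interpreted.** Protocol 9.4.7 says of αGAL that "it is a normal component of breast milk and it is possible that the women enrolled in the study naturally produce" it, and that the assay cannot distinguish it from Fabrazyme. SAP 2.1.5 repeats the assay limitation. No milk exists from before therapy, so "breast milk samples will be tested just prior to the Fabrazyme infusion and at timed intervals as specified above", with the aim of seeing whether the level rises. The synopsis, under its statistical plans, adds: "Each lactating woman will serve as her own control, with pre-infusion and post-infusion breast milk samples".

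**What is to be calculated.** Protocol 9.3 and SAP 2.1.5 list Cmax in plasma and milk, AUC0-2 in plasma and milk, the amount in milk (activity times volume), lactation clearance over 0-2 hours (amount divided by AUC) and the milk/plasma AUC0-2 ratio. Protocol 9.3 has each AUC "calculated using the trapezoidal method from 0 to 2 hours post end of infusion". Protocol 11.10 takes the ratio "from time 0 (sample 2) to 2 hours after the end of infusion (sample 3". In its lactation clearance paragraph the same section says "Breast milk will be collected at Baseline (sample 1) to empty each breast of milk" and "AUC from Baseline to 2 hours after the end of infusion will be calculated using a linear trapezoid".

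**What is to be presented.** Protocol 11.8 and SAP 2.1.4 list the αGAL level together with "volume, and fat and protein content in breast milk samples", without naming sample times or a change. SAP 2.4.6 gives descriptive statistics of the PK parameters by visit. SAP 2.4 switches to listings if fewer than 5 mothers enroll. SAP 3 announces an interim analysis of milk αGAL activity and gives no method.

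**What cannot be seen.** The protocol's interim text is redacted in the synopsis and in 11.9, its bioanalytical text in 9.3 is blank, and SAP 2.4.5.6 shows only a heading. The visible SAP counterparts (2.1.5 and 3) contain no comparison with sample 1.

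**The concern.** The protocol explains why a single milk activity value is ambiguous and names the remedy: compare it with the same mother's pre-infusion milk. The calculations then leave the remedy out. No stated parameter subtracts sample 1, divides by it or is compared with it, and the milk/plasma ratio does not use sample 1 at all.

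Protocol 6.2 gives as the reason for the study that excretion of Fabrazyme in milk is unknown. Terms such as amount excreted and lactation clearance will be read as describing drug. Where natural enzyme is measurable, part or all of those figures could be the mother's own enzyme, and the report would have no pre-specified quantity to tell the two apart.

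**Working it through.** The study is descriptive and states no power or sample size calculation, so there is no figure to reproduce. The check applies the documents' own formulas.

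**Inputs.** Quantification limit 1.38 ng/mL (SAP 2.1.5). Everything else is assumed for illustration: samples 2 and 3 both 6.9 ng/mL (5 × 1.38), milk volume 60 mL, plasma AUC0-2 1,200 ng·h/mL. Protocol 11.10 models lactation clearance on renal clearance, so I take its denominator to be the plasma AUC.

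**1. Parameters as stated**
- Milk Cmax = 6.9 ng/mL
- Milk AUC0-2 = (6.9 + 6.9)/2 × 2 = 13.8 ng·h/mL
- Amount = 6.9 × 60 = 414 ng (207 ng at 30 mL, 828 ng at 120 mL)
- Lactation clearance = 414/1,200 = 0.345 mL/h
- Milk/plasma ratio = 13.8/1,200 = 0.0115

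**2. The same post-infusion values with three different pre-infusion values.** The step 1 results are identical in all three rows. The shares from drug assume stable natural activity and no residual drug in sample 1.

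| Sample 1 (ng/mL) | Share from drug | Difference (ng/mL) | AUC0-2 less sample 1 (ng·h/mL) | Amount less sample 1 (ng) |
|---|---|---|---|---|
| 6.9 | none | 0 | 0 | 0 |
| 3.45 | half | 3.45 | 3.45 × 2 = 6.9 | 3.45 × 60 = 207 |
| below 1.38 | all, if natural activity is nil | 5.52 to 6.9 | 11.04 to 13.8 | 331.2 to 414 |

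The last row is a range because sample 1 may lie anywhere from 0 to 1.38: 6.9 − 1.38 = 5.52 and 6.9 − 0 = 6.9. If all three samples are below the limit, the difference is only known to lie between −1.38 and 1.38 ng/mL.

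**3. No transfer, over a range of natural activity.** At 1, 5 and 10 times the limit, milk AUC0-2 is 2.76, 13.8 and 27.6 ng·h/mL, and the amount in 60 mL is 82.8, 414 and 828 ng.

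**4. Different assumed inputs.** Take milk flat at 10 ng/mL, volume 50 mL, and plasma 1,000 then 400 ng/mL, so plasma AUC0-2 = (1,000 + 400)/2 × 2 = 1,400. Milk AUC0-2 is 20, the ratio 20/1,400 = 0.0143, the amount 500 ng and clearance 500/1,400 = 0.357 mL/h, whether sample 1 is 10, 5 or 0. The differences are 0, 5 and 10 ng/mL.

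**5. The clearance interval.** Let P1, P2 and P3 be the plasma values at samples 1 to 3 and T the infusion length in hours.
- Protocol 9.3 and SAP 2.1.5, 0-2 h: AUC = (P2 + P3)/2 × 2.
- Protocol 11.10, Baseline to 2 h after infusion: AUC = (P1 + P2)/2 × T + (P2 + P3)/2 × 2.

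In 11.10, Baseline means sample 1 of that visit and time 0 means sample 2, so these are different intervals. The denominators differ by (P1 + P2)/2 × T. The matching milk volume differs too: the sample 3 collection alone, or samples 2 and 3 together. Neither version subtracts sample 1.

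**The case against.** The strongest reply is that the comparison is planned and only its format is missing. Protocol 9.4.7 states its purpose, and the own-control sentence stands in the synopsis under the statistical plans, next to the list that names milk αGAL. Levels will be summarized or listed, and milk volume is explicitly summarized by timepoint. With about 10 mothers and no hypothesis testing, a reader who has levels by sample time can see the contrast. Protocol 11.10 says that characterizing PK is not an objective, and no text claims that Cmax, AUC or the ratio will prove transfer.

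Much of this stands. The data are collected, so the gap is in the analysis. It does not close the point, because display of αGAL by sample time is not stated, and the parameters that are defined omit the contrast that gives them meaning.

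It is also fair that the illustration is constructed. Samples 2 and 3 are fixed, so identical outputs are guaranteed, and the documents give no natural milk level. The arithmetic shows what the formulas cannot distinguish; it does not estimate what will happen.

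A reader might infer that Objective 1 cannot be met. The documents do not support that: the objective asks whether activity is present, which total activity answers. A reader might also infer that neither document defines the comparison anywhere. That goes too far, because the protocol's interim text is redacted and the statement can cover visible text only.

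**Conclusion.** The point holds for the visible text. The documents base interpretation on a rise over sample 1, and no visible analysis section computes or displays that rise. If natural milk activity is at or above 1.38 ng/mL, milk Cmax, AUC0-2, amount, clearance and milk/plasma ratio are all positive with zero transfer and cannot by themselves show it. Under the assumed inputs, one set of results (13.8 ng·h/mL, 414 ng, 0.345 mL/h, 0.0115) fits a drug share of none, half or all. If natural activity is below the limit, the problem does not arise.

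It would be wrong to conclude that the study will report false transfer, because that depends on a natural level that the documents do not give. It would also be wrong to treat the value after subtraction as the drug content of milk. Sample 1 comes from a mother who may already be on Fabrazyme and may hold residual drug. If residual drug is R and the rise is D, subtraction recovers D/(D + R): 91%, 67% or 50% for R equal to 10%, 50% or 100% of D (assumed).

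The missing comparison is a cheap improvement. The clearance interval is a separate matter and is wrong as written, since the two definitions cannot both be followed.

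**What to change.** 1. In SAP 2.1.5 and 2.4.6, present milk αGAL by sample time (1, 2, 3) for each mother and visit. Make the same-visit differences of samples 2 and 3 from sample 1 the main descriptive measure of drug transfer, with no threshold and no test.
2. For values below 1.38 ng/mL, show the difference with the value set to 0 and set to 1.38. Leave negative differences as they are. With zero transfer, setting them to 0 would bias the mean upward by √2 × CV/√(2π) of the natural level, which is 5.6% to 11.3% for an assumed assay CV of 10% to 20%.
3. Report milk AUC0-2 and amount both as stated and with sample 1 subtracted. Label lactation clearance and the milk/plasma ratio as based on total αGAL activity, not drug.
4. Reconcile the clearance interval across Protocol 9.3, Protocol 11.10 and SAP 2.1.5, and use the milk volumes that the synopsis records for that same interval.
5. Limit conclusions about Fabrazyme to an increase above the pre-infusion sample. State that sample 1 may hold residual drug, and that emptying the breast at sample 1 may itself change activity in later samples.

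The cost is SAP text, a few derived variables and one reconciled definition in the protocol. No new samples are needed, since sample 1 is already taken at Months 1, 3 and 6. The drawback is that differences will be noisy near the quantification limit.
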